A randomized controlled trial comparing cosmetic outcomes of pediatric laceration closure using a tissue adhesive (Dermabond™) versus adhesive strips (Steri-Strips™) versus absorbable sutures

Study Protocol

NCT ID: NCT03280628

Document Date: 8/10/2017

Principal Investigator:
[name], MS
Vanderbilt University Medical Center
Pediatric Emergency Medicine
[name]
[name]

Table of Contents		
Section	Topic	Page
I	Specific Aim and Study Hypothesis	3
II	Summary of Approach	3
III	Background	3
IV	Rationale	4
V	Inclusion and Exclusion Criteria	4
VI	Subject Recruitment and Enrollment	4
VII	Study Procedures	5
VIII	Predictor Variables	5
IX	Outcome Variables	6
Χ	Ethical Considerations	7
ΧI	Risks of Study Participation	7
XII	Reporting of Adverse Events or Unanticipated Problems involving Risk to Subjects or Others	7
XIII	Study Withdrawal or Discontinuation	7
XIV	Data Management	8
XV	Statistical Considerations	8
XVI	Privacy and Confidentiality Issues	8
XVII	Follow-up and Record Retention	9
XVIII	Data Safety and Monitoring Plan	9
XIX	References	9

I. Specific Aim and Study Hypothesis

Specific Aim: The specific aim of this study is to determine the best of 3 different methods of closure of simple pediatric lacerations in terms of cosmetic outcome, pain, need for sedation, cost and length of ER stay.

Hypothesis: We hypothesize that the closure of simple pediatric lacerations with either a tissue adhesive (DermabondTM), or adhesive strips (Steri-StripsTM) will provide clinically equivalent cosmetic outcomes to absorbable sutures while reducing pain, need for sedation, cost and length of ER stay without increasing the risk of complications.

II. Summary of Approach

To address the Specific Aim we will conduct a 3-arm randomized controlled trial comparing methods of closure of simple pediatric lacerations. The 3 arms will be: DermabondTM, Steri-StripsTM, and absorbable sutures (our control arm).

We will examine the association between closure method and the primary outcome variable, cosmesis of the resultant scar.

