Depending on which arm they are randomized to, participants will have their laceration closed by either DermabondTM, Steri-StripsTM, or absorbable sutures per the treatment arm protocols (Protocols, see Appendix IV). Unfortunately, given the nature of the study, neither the patient, parent nor health care provider will be blinded to the method of closure. Additional topical or injected anesthetics or the use of sedation will be left up to the patient/parent and provider's discretion. After the procedure, both patient (if older than 3 years old) and parent/guardian will be asked to fill out a short questionnaire (Questionnaires, see Appendix VI). The parent/guardian will be asked to rate the appearance of 3 images of random scars. All parents/guardians in the study will rate the same 3 scars to establish a baseline for each parent. The health care provider will also be asked to fill out a short questionnaire (Questionnaires, see Appendix VI). Upon discharge, the participant and their parent/guardian will be provided with verbal and written return precautions by the study staff (Care Instructions, see Appendix V).

Parents/guardians will be called 3 months after their initial visit for a brief over-the-phone interview (Questionnaires, see Appendix VI). At this time, they will be prompted to take a picture of the scar and send it to the Investigator by e-mail. A Vanderbilt email address has been set-up and is secure per Vanderbilt criteria. As an alternative, they can come back to the VCH ED where study staff will ask them a couple of questions in person and take a picture of the scar.

Every effort will be made to de-identify the images of the scar (using image editing software to crop everything on the image but the scar with some surrounding skin). The images will then be collected and presented to two Plastic Surgeons who will be blinded to the method of closure. They will subsequently score the scar as seen in the images (Questionnaires, see Appendix VI). All data will be collected on paper and then transferred to REDCap®. Each piece of data will be transferred to REDCap® by two study staff independently and then examined for any differences which can be reconciled by examining the paper forms. This will prevent errors in transferring data from paper to electronic format.

Participants will be compensated with a \$15 check after completion of the 3 month questionnaire and sending of photo.

Randomization

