Randomization will be accomplished using randomizer.org software to generate a set of 90 numbers from 1 to 3 for 90 enrolled participants. Each digit from 1 to 3 will correspond to a study arm.

Data Acquisition

Study data will be acquired through the means of the aforementioned questionnaires (Questionnaires, see Appendix VI), phone interviews, and by simple chart review. The secondary outcome of "cost of visit" will be acquired through Medical Records.

Institution/Hospital: Vanderbilt Children's Hospital

VIII. Predictor Variables

Predictor variables are the 3 treatment allocation arms: Dermabond[™], Steri-Strips[™], and absorbable sutures. Other independent variables to be collected include demographics of the patient (age, sex, race/ethnicity), specifics of the laceration (location, length and width, time between trauma and wound closure) and level of training of the provider who will be closing the wound. Demographics will be extracted from the patient Electronic Medical Record and from the parent Questionnaire (Questionnaires, see Appendix VI). Both the specifics of the laceration and the level of training of the provider will be extracted from the provider questionnaire at the time of the procedure (Questionnaires, see Appendix VI).

IX. Outcome Variables

a. Primary outcome variable

The primary outcome will be cosmesis of the resultant scar as measured on a 100 mm Visual Analogue Scale where a score of 0 corresponds to "worst scar" and a score of 100 corresponds to "best scar." This scale has been validated as a scoring method to evaluate cosmesis of a scar. 12, 16, 17, 23, 32 Due to its sensitivity and the fact that it provides parametric data, the scale allows for smaller, more practical sample sizes to show clinically-significant differences in populations. 12, 16, 17, 23, 32 The Visual Analogue Scale will be used by two Plastic Surgeons blinded to closure method to rate a patient's scar at 3 months. In addition, parents will be asked to rate the scar on a scale of 0 to 100 during their over-the-phone interview at 3 months. We will compare their rating of their child's scar to the average of their ratings of the 3 images of random scars at the initial visit.

b. Secondary outcome variables

i. Pain experienced by patient

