This secondary outcome will be evaluated by the patient (if age-appropriate), parent and provider at the time of the ER visit (Questionnaires, see Appendix VI). Patients aged 3 to 12 will be asked to rate their pain on a Wong-Baker FACES® Pain Rating Scale (licensing for use in progress). Patients aged 12 to 18 will be asked to rate their pain using a 100 mm Visual Analogue Scale with a score of 0 corresponding to "No pain" and a score of 100 corresponding to "Terrible pain." Parents and providers will each be asked to score how much pain they felt the patient experienced on the same Visual Analogue Scale.

ii. Need for anesthetics/anxiolytics/sedation

This secondary outcome examines the need for adjuncts to control pain/anxiety including LET, injected lidocaine, anxiolytics or systemic pain medications, ketamine sedation or others. Data will be collected by study staff observing the procedure. Data will also be extracted from the patient's Electronic Medical Record.

iii. Length of procedure

This secondary outcome, measured in minutes, will be collected by study staff observing the procedure.

iv. Cost of visit

This data will be extracted from the patient's Electronic Medical Records and from the Billing Department.

v. Length of ER stay

This data will be extracted from the patient's Electronic Medical Records.

vi. Resource utilization

Institution/Hospital: Vanderbilt Children's Hospital

This secondary outcome examines the need for personnel in the room to keep the child calm or still. This data will be collected by study staff observing the procedure.

vii. Likelihood that parent would recommend wound closure type

This secondary outcome will be measured using a 100 mm Visual Analogue Scale with a score of 0 corresponding to "Extremely unlikely" and a score of 100 corresponding to "Extremely likely." This data will be extracted from the parent questionnaire at the time of the ED visit (Questionnaires, see Appendix VI).

viii. Complications

Prevalence of complications (infection, dehiscence, etc.) will be evaluated. This secondary outcome will be obtained during the brief phone questionnaire with parents at 3 months after the ED visit (Questionnaires, see Appendix VI).

ix. Poor cosmetic outcome

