This secondary outcome will be extracted from the Visual Analogue Scales used to rate a patient's scar, as evaluated by both the parent and Plastic Surgeons blinded to method of closure (Questionnaires, see Appendix VI). A score less than 35 mm on the 100 mm scale will be considered "poor cosmetic outcome" as used in previous studies.

x. Presence of train tracks

This secondary outcome will be extracted from the Plastic Surgeon questionnaire at 3 months (Questionnaires, see Appendix VI).

X. Ethical Considerations

DermabondTM and Steri-StripsTM are both FDA-approved methods of laceration closure and there have been no studies demonstrating the inferiority of these closure methods compared to sutures, the traditional method of laceration closure. Thus, randomizing patients to either DermabondTM or Steri-StripsTM treatment arms does not violate the principle of equipoise.

XI. Risks of Study Participation

Surveillance for medical risks, including but not limited to infection and dehiscence, will be performed during the study of each subject by [name] [name].

The specific aim of this study involves the collection of Personal Health Information (PHI). HIPAA regulations pertaining to subjects' PHI will be reviewed with the Vanderbilt IRB and assurance of conformity to these regulations and protection of PHI provided. As noted, we are taking steps to protect this information. Study staff are required to honor and preserve patient confidentiality and privacy at all times and in all management of data and data files. All completed subject information forms will be initially placed in a locked box in the VCH ED after enrollment and data collection. Forms will then be promptly transferred to individual patient files and maintained in a locked data collection box in a locked office in order to maintain confidentiality and security of data. Photos will be e-mailed to a secure Vanderbilt e-mail. Access to computer files will be further restricted by file passwords. The database will be maintained on REDCap®.

XII. Reporting of Adverse Events or Unanticipated Problems involving Risk to Subjects or Others

Any unexpected problems involving risks to subjects or others will be immediately reported to the Institutional Review Board of Vanderbilt University within ten days using the IRB form #1105.

XIII. Study Withdrawal or Discontinuation

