After the parents have signed the consent form, and the patient has signed the assent form as applicable, one copy will be given to the parents and one copy will be kept by [name] [name] in a locked data collection box in a locked office. All efforts, within reason, will be made to keep protected health information (PHI) private. PHI is health information that is or has been gathered or kept by Vanderbilt as a result of a subject's healthcare. This includes data gathered for research studies, and can be traced back to the subject. Using or sharing ("disclosure") such data must follow federal privacy rules. By signing the consent for this study, subjects are agreeing ("authorization") to the uses and possible sharing of PHI. If a patient or their parent/guardian decides to be in this research study, he/she is also agreeing to let the study team use and share PHI as described below.

As part of the study, [name] [name] and her study team may share the results of a subjects' study-linked questionnaires and photos, as well as parts of the medical

record, to the groups named below. These groups may include people from the Federal Government Office for Human Research Protections, the Vanderbilt University Institutional Review Board, and insurance companies for billing purposes. Federal privacy rules may not apply to these groups; they have their own rules and codes to assure that all efforts, within reason, will be made to keep PHI private.

[name] [name] may give health data, without a subject's name, to others or use it for other research projects. Vanderbilt and [name] [name] and her staff will keep each subject's PHI in strict confidence, and will comply with any and all laws regarding the privacy of such information.

XVII. Follow-up and Record Retention

Research data will not be kept in a subject's medical record. Deidentified study results will be kept for up to 5 years after the study is finished but all identifying data will be destroyed once the study is finished.

XVIII. Data Safety and Monitoring Plan

Surveillance for medical risks, including but not limited to infection and dehiscence, will be performed during the study of each subject by the study investigators. Any adverse events will be reported as per IRB guidelines.

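### The complications outcome has a single named source, the 3-month parent report, not linked to the promised surveillance or chart review, and 30 children per arm cannot show that risk is not increased

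*Combined protocol and SAP*

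**What the plan says.** Section I (hypothesis) expects both adhesive methods to match sutures on cosmesis "without increasing the risk of complications". Section IX.b.viii defines the matching secondary outcome: "Prevalence of complications (infection, dehiscence, etc.) will be evaluated", followed by "This secondary outcome will be obtained during the brief phone questionnaire with parents at 3 months after the ED visit". No other source, time point or missing-data rule is given for it.

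Other sections bear on the same events:

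- Section VII, Study Design, on the 3-month contact: "As an alternative, they can come back to the VCH ED", where staff put the questions in person. It also states that patient, parent and provider are not blinded.
- Section VII, Data Acquisition, lists questionnaires, "phone interviews, and by simple chart review" as the study's general sources.
- Section XI: "Surveillance for medical risks, including but not limited to infection and dehiscence, will be performed during the study of each subject". Section XVIII repeats this, says that it "will be performed during the study of each subject by the study investigators", and adds: "Any adverse events will be reported as per IRB guidelines".

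Section XV sizes the trial on cosmesis only, at 30 children per arm. It allows for dropouts and missing data without stating a rate. No margin, test or interval is given for complications.

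**The concern.** The hypothesis makes a safety claim, and the outcome that would support it depends on one contact. If that contact fails, the outcome is blank. If it succeeds, the value is an unblinded parent's recollection of events that may have happened weeks earlier. The plan promises surveillance and chart review, but does not say that either feeds the outcome. An infection treated at the same hospital could therefore be in the record and absent from the analysis.

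The second issue is inferential. With no rule for what result would support the hypothesis, a low count or a non-significant comparison could be taken as support, although arms of this size cannot exclude a substantial increase.

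**Working it through.** **1. Sources named for each outcome (Section IX.b)**

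| Outcome | Named source |
|---|---|
| ii. Anesthetics, anxiolytics, sedation | Staff observation and electronic medical record |
| iv. Cost of visit | Electronic medical record and billing |
| v. Length of ER stay | Electronic medical record |
| viii. Complications | 3-month parent questionnaire only |

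Where the plan means to use the record for an outcome, it says so. For complications it does not. The surveillance sentences in XI and XVIII give no schedule, method, form or link to outcome viii. The only scheduled contact after discharge is the 3-month call or the visit that replaces it. So, as written, a child whose family makes neither contact has no value for outcome viii.

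**2. The plan's own sample size figure**

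Section XV requires 5 to 21 per group for cosmesis (one-way ANOVA, 90% power, alpha 0.05). The 21 reproduces exactly with three groups, means 0, 0 and 15 mm, and SD 15 mm. The squared deviations from the mean of 5 sum to 25 + 25 + 100 = 150, so the noncentrality is 21 × 150/225 = 14, and 21 is the smallest n reaching 90% power. It is a cosmesis requirement and has no bearing on complications. The planned count used below is the 30 recruited per arm. No blocking is stated for the randomization list, so exactly 30 in each arm is itself an assumption.

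**3. Precision with complete follow-up**

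With 0 events in n children, the exact two-sided 95% upper limit is 1 − 0.025^(1/n). At n = 30 this is 1 − 0.025^(1/30) = 11.6%. That limit is for one arm's rate. The hypothesis concerns a difference, which carries the uncertainty of both arms.

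**4. Power of a pairwise comparison**

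The documents give no complication rate, so the rates here are assumptions. Power is the sum of binomial probabilities over all pairs of counts with two-sided Fisher p ≤ 0.05, at 30 per arm.

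| Assumed rates | Power at 30 per arm | n per arm for 80% power (normal approximation) |
|---|---|---|
| 5% v 10% | 2% | 435 |
| 5% v 15% | 9% | 141 |
| 5% v 20% | 24% | 76 |

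**5. What a non-significant result could hide**

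Suppose the suture arm has 0 of 30 events and an adhesive arm has k of 30. The two-sided Fisher p is 2 × C(30,k)/C(60,k).

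- k = 5: 2 × 142,506/5,461,512 = 0.052, not significant.
- k = 6: 2 × 593,775/50,063,860 = 0.024, significant.

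An observed 5/30 = 16.7% against zero would thus fail the test.

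**6. Effect of unknown status**

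With all 30 as denominator, each child of unknown status widens the possible range of that arm's rate by 1/30 = 3.3 percentage points. The number of such children cannot be predicted, because no dropout rate is stated.

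**The case against.** The strongest reply is that the plan does look for complications elsewhere. XI and XVIII commit the investigators to surveillance of each subject, adverse events go to the IRB, chart review is a study source, and families leave with written return precautions. Loss is also guarded against: families with no way to photograph and e-mail who also cannot return are excluded, payment follows completion of the 3-month contact, and an in-person route exists. The appendices with the questionnaires and data forms are not in the text available here, so what they record cannot be judged. Finally, complications are one of ten secondary outcomes, and low power for an uncommon event is ordinary in a 90-child trial.

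Much of this stands, and it rules out three stronger readings:

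- A reader might infer that unreached families have no safety data at all. The documents do not support that, because surveillance and event reporting are promised. What is missing is a value for the analysed outcome.
- A reader might take 21 of 30 as expected retention, or 30% as the planned loss. The 21 is the upper end of a cosmesis sample size range, and no dropout rate is stated.
- A reader might infer that missed calls make complications look rarer. Families with a problem could be less willing to respond, or more. A shortfall that acts equally in every arm would lower the rates but leave their ratio unchanged. Direction and size are unknown.

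Nor do the documents say that a non-significant result will be reported as no increase. The point is that no rule prevents it. The reply does not supply the missing link between the promised surveillance and outcome viii, or make the hypothesis demonstrable at 30 per arm.

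**Conclusion.** The point holds as a cheap improvement. Outcome viii rests on one unblinded parent report at 3 months, and the surveillance and chart review promised elsewhere are not tied to it. A family not reached has no complications value, whatever the hospital record shows. How many children this affects, and which way it would push the comparison, cannot be determined from the documents.

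The limit on the safety claim does not depend on any loss. With all 30 followed and no events, a rate of up to 11.6% in that arm remains compatible with the data. Power of about 9% rests on the assumed 5% v 15%; across the assumed comparators of 10% to 20% against 5%, it runs from 2% to 24%. The trial can describe complications and bound the possible increase. It cannot show that there is none.

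**What to change.** 1. **Source.** Reword IX.b.viii so that a complication counts if it is reported at the 3-month contact or recorded in the VCH electronic medical record between the ED visit and 3 months. Review the record for every randomised child, on the same form in all arms, and before the identifiers are destroyed under Section XVII. Name this review in XI and XVIII as the surveillance meant there.
2. **Unknown status.** Report by arm the number reached, the number with record data only, and the number unknown. In the main analysis, do not count a child who was not reached and has no later VCH record as complication-free. Add a sensitivity analysis with all randomised children as denominator and the unknowns set each way.
3. **Inference.** Report each adhesive-minus-suture difference with an exact 95% confidence interval, by a method named in advance. In Section I, replace the claim of no added risk with a statement of the largest increase that the interval leaves possible. State that a non-significant test will not be reported as no increase.

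The cost is protocol wording and a short chart review for 90 children whose records are already opened for other outcomes. No visit, treatment or sample size changes. Care outside VCH is still missed unless the parent reports it, so the 3-month contact stays as a source. The safety claim becomes more modest.

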As a secondary aim we will assess for statistically significant differences in the degree of pain experienced by the patient, in the need for sedation, in the cost of each closure method, and in the length of the patient's ER stay. We anticipate that the treatment arms (DermabondTM, Steri-StripsTM) will demonstrate no clinically significant difference in cosmetic outcomes while reducing the pain experienced by patients during laceration closure, reducing the need for sedation, reducing costs and reducing the length of patients' ER stays.

III. Background

Lacerations are a very common presentation in pediatric Emergency Departments (ED). In fact, over the past 2 years (February 2015-2017), there were a total of 3100 lacerations repaired in the ED at Monroe Carell Jr's Children's Hospital at Vanderbilt (VCH). This can be a painful and traumatic procedure for children, especially young children. Given that most lacerations occur in young children (74.1% in those less than 6 years old), it is important to use noninvasive and painless closure methods when possible. ^{10, 11, 15}

Historically, sutures have been the preferred method of closure for lacerations.¹⁸ While they have been made of different materials over the years, the general concept of needle and string has remained mostly consistent.¹⁸ However, new methods of wound closures have been developed since. Surgical tape was first developed by surgeon Horace Day in 1845.⁵ The earliest versions of surgical tape had several issues including proper adhesion, skin irritation, blocking of perspiration, etc.⁵ The modern version of surgical tape that we are now familiar with (Steri-StripsTM) has been around since the 1960s, and except for a few minor modifications, it has largely gone unchanged.³⁵

Tissue adhesives, derived from cyanoacrylate, were invented in the 1940s and have been used for decades for wound closure outside of the United States.³ However, it wasn't until 1998 that the Food and Drug Administration approved 2-octyl cyanoacrylate (DermabondTM) for use in the United States.³⁶

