Patients and their parent/guardian(s) will be told very explicitly by the investigators that their participation in this research investigation is entirely voluntary and that they may withdraw at any time. We will further emphasize verbally and in the informed consent document that a decision on the part of the patient or parent/guardian(s) to not participate will in no way change, compromise or jeopardize the patient's care. Indeed, we anticipate that a number of eligible patients will not be enrolled on this basis.

XIV. Data Management

Participants' information (Subject Enrollment Form, see Appendix II, Questionnaires, see Appendix VI, pictures) will be kept in a separate file for each subject. Data will be transferred to the REDCap® server. This data will then be sent for statistical analysis.

XV. Statistical Considerations

We are planning a study of a continuous response variable from independent control and experimental subjects with 1 control per experimental subject. In previous studies, the response within each subject group was normally distributed with a standard deviation of 15 mm on a 100 mm Visual Analogue Scale and the minimal clinically important difference between two scars was 15 mm on a 100 mm Visual Analogue Scale. We performed multiple sample size power calculations using STATA® 14.1 (College Station, Texas). Using one-way ANOVA, with a power of 90% and an alpha of 0.05, we would need between 5 and 21 subjects per group to detect a clinically significant difference of 5 to 15 mm between groups depending on the standard deviation in each group (in anticipation of the fact that we may have a larger standard deviation). In order to assure an effective sample size after accounting for dropouts and missing data, we propose to recruit 30 experimental subject per treatment arm and 30 control subjects, for a total of 90 subjects.

XVI. Privacy and Confidentiality Issues

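### Section XV labels between-group scar differences of 5 to 15 mm clinically significant, although its own stated minimum is 15 mm

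*Combined protocol and SAP*

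**What the plan says.** Section XV (Statistical Considerations) takes two facts from previous studies. On spread, "the response within each subject group was normally distributed with a standard deviation of 15 mm on a 100 mm Visual Analogue Scale". On importance, "the minimal clinically important difference between two scars was 15 mm on a 100 mm Visual Analogue Scale".

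The sizing sentence, based on a one-way ANOVA at 90% power and alpha 0.05, puts the requirement at 5 to 21 in each arm. It gives the purpose of that size as follows: "to detect a clinically significant difference of 5 to 15 mm between groups depending on the standard deviation in each group". The reason offered for letting the figures vary is a precaution, made "in anticipation of the fact that we may have a larger standard deviation". Recruitment is then set at 30 per arm, 90 in total, to allow for dropout and missing data.

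Section I hypothesizes that each adhesive method is clinically equivalent to absorbable sutures in cosmesis. Section II expects that the adhesive arms "will demonstrate no clinically significant difference in cosmetic outcomes". Neither section attaches a number. Section IX uses 35 mm to classify a single scar as a poor outcome, which is not a threshold for a difference between arms.

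**The concern.** If 15 mm is the smallest difference that matters, a difference of 5 to 14 mm is not clinically significant. The sizing sentence gives that label to the whole range from 5 mm up. The standard deviation cannot reconcile the two statements: a larger one makes a given difference harder to detect, but does not change whether patients or parents would care about it.

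The label matters because the primary conclusion is worded in it. Suppose an adhesive arm scores 10 mm worse than sutures and the difference is statistically significant. Measured against the stated minimum, the authors could report no clinically significant difference. Citing the sizing sentence, they could report a clinically significant one. The choice would be made after the data are seen.

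**Working it through.** **Inputs from Section XV:** SD 15 mm, three groups, one-way ANOVA, power 90%, alpha 0.05, 5 to 21 per group stated as needed, 30 per arm recruited. **Assumptions of this check:** the pattern of means, the true differences, and SD 20 as an example of the larger SD that the plan anticipates without giving a value.

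**1. Which difference does the stated size support?** ANOVA power comes from the noncentral F distribution with λ = n·Σ(μᵢ − μ̄)²/SD². If one arm differs by d, then Σ(μᵢ − μ̄)² = 2d²/3.

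- d = 15, SD 15: λ = 0.667n. At n = 20, λ = 13.33 and power is 0.8997; at n = 21, λ = 14.0 and power is 0.915. The requirement is **21 per group**, the plan's upper figure.
- d = 5, SD 15: λ = 0.0741n. At n = 172, λ = 12.74 and power is 0.900. The requirement is **172 per group**.
- With 30 per arm, power is 0.98 at 15 mm (λ = 20) and 0.24 at 5 mm (λ = 2.22).

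With equally spaced means (0, d/2, d), the requirements are 27 per group at 15 mm and 229 at 5 mm. Even if 5 mm is taken as the step between adjacent arms, so that the outer arms differ by 10 mm, 58 per group are needed.

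The figure 21 also arises at 5 mm if the SD is about 5.1, but the plan states 15 and expects, if anything, more. The lower figure, 5 per group, does not reproduce at SD 15 or above: at d = 15 it needs an SD of about 5.8 to 6.8 under the first two patterns.

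**2. When is a pairwise difference statistically significant?** SE = SD·√(2/n) = 15·√(2/30) = 3.87 mm. With the pooled ANOVA variance, df = 3(30 − 1) = 87 and t₀.₉₇₅ = 1.988. The smallest significant difference, with no multiplicity adjustment, is 1.988 × 3.87 = **7.70 mm**.

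**3. How often is the result significant yet below 15 mm?** For a true difference δ, the probability is Φ((15 − δ)/SE) − Φ((7.70 − δ)/SE), plus the matching term on the negative side.

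| True difference (assumed) | Calculation | Probability |
|---|---|---|
| 0 mm | 2 × [Φ(3.87) − Φ(1.99)] | 5% |
| 5 mm | Φ(2.58) − Φ(0.70) | 24% |
| 8 mm | Φ(1.81) − Φ(−0.08) | 50% |
| 10 mm | Φ(1.29) − Φ(−0.59) | 63% |

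The negative-side term is below 0.1% in the last three rows.

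**4. Sensitivity at a true 10 mm.** With 21 per arm analysed, SE = 4.63, the significance limit is 9.26 mm and the probability is 42%. With SD 20 and 30 per arm, SE = 5.16, the limit is 10.26 mm and the probability is 31%.

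**The case against.** The strongest defence is that the plan defines importance once. Only 15 mm is called a minimum, and the 5 to 15 mm range appears where several power runs are being reported, so the adjective may simply be loose. Nothing in the documents makes 5 mm a rule for reading results. This stands in part. A reader might infer two rival definitions of equal standing, but the documents do not support that: the explicit minimum and the stated size both favour 15 mm. What remains is a label that contradicts that minimum.

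The two figures also have different objects: 15 mm is stated for two scars, the range for groups. A difference that matters for one scar need not be the one that matters for arm means. The plan does not draw this distinction. If it was intended, the plan has no single threshold for means at all.

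A reader might also count every observed difference from 5 to 15 mm as open to opposite verdicts, which at SD 15 and 30 per arm gives 20%, 50%, 75% and 80% at true differences of 0, 5, 8 and 10 mm. That overstates the problem, because it includes differences below 7.70 mm that are not statistically significant. The narrower figures in the table measure the reporting risk. Where the true difference is near zero, as the plan anticipates, that risk is about 5%.

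**Conclusion.** The label on values below 15 mm is wrong as written, and the plan's primary cosmetic conclusion depends on the term. This is an inconsistency in the threshold for interpretation. It does not show that the trial is too small for 15 mm: 30 per arm gives ANOVA power of about 0.94 to 0.98 there at SD 15.

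The consequence is small if the arms are truly alike and substantial if they differ moderately: about 5% at no difference, rising to 63% at 10 mm. These figures assume SD 15, 30 analysed per arm, normally distributed estimates and no multiplicity adjustment, which would raise the 7.70 mm limit and lower the probabilities. The documents say nothing about which true difference is likely beyond expecting none that matters clinically.

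**What to change.** Before analysis:

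- **Threshold.** State one between-arm threshold, by default the plan's own 15 mm, and say explicitly that it is applied to arm means. If the authors think a smaller value suits means, they should justify it and restate the sizing to match.
- **Section XV.** Size for that threshold and report the SD and pattern of means used. Call any smaller value in the power runs a *detectable difference* only.
- **Sections I and II.** Tie both the equivalence hypothesis and the expected absence of a clinically significant difference to the same threshold.
- **Decision rule.** Claim no clinically significant difference only if the whole 95% confidence interval for adhesive minus suture lies within plus or minus the threshold.

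At 15 mm the rule is workable with the planned size. The half-width at SD 15 and 30 per arm is 7.70 mm, so the estimate must lie within 15 − 7.70 = 7.30 mm of zero. If there is no true difference, that happens with probability 2Φ(7.30/3.87) − 1, about 94%. At 5 mm it could not be met at that SD and size, because the half-width alone exceeds the threshold.

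The cost is wording in three sections, with no added patients or data if 15 mm is kept. The downside is that a statistically significant difference below the threshold can no longer be called clinically significant, so it should still be reported with its confidence interval. A 14 mm deficit, for example, would have an interval of about 6.3 to 21.7 mm, and the rule would also bar a claim of no clinically significant difference.
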